Type of Visit	In-Person Site or Home Health Visit with Telehealth	In-Person Site Visit	In-Person Site or Home Health Visit	Telehealth Visit	In-Person Site, Home Health or Telehealth Visit	Telehealth Visit	In-Person Site, Home Health or Telehealth Visit	In-Person Site, Home Health or Telehealth Visit	
Weight, height	X		X						
 
Height may be self-reported.
 
HD treatment days will require database entry of pre- and post-dialysis weight. See Section 8.3.2.
 

LABORATORY									
Hematology	[X]	X	X		[X]		[X]	[X]	
 
Screening visit: Laboratory assessments are not required at screening unless deemed necessary by the investigator to confirm eligibility. The medical laboratory test abnormalities within 3 months prior to screening must be closely assessed.
 
Screening visit: If Laboratory assessments cannot be verified within 3 months of screening, local laboratory testing should be performed at screening to confirm eligibility for the study.
 
Baseline laboratory assessments should be collected prior to first dose of study intervention.
 
SARS-CoV-2 serology sample should be collected if an in-person (in clinic or home health) visit is conducted at Day 14±2, Day 34±3 or ET visits.
 
Safety laboratory tests (hematology, blood chemistry) at Days 14±2 and 34±3/ET are required only if clinically significant abnormal laboratory values were present from a sample drawn at the previous study visit when laboratory assessments were performed.
 
Abnormal laboratory values related to AEs should be followed until resolution. See Section 8.3.4 and Appendix 2.
 

Blood chemistry	[X]	X	X		[X]		[X]	[X]	
SARS-CoV-2 Serology (IgG and IgM)	[X]	X	X		[X]		[X]	[X]	

PFIZER CONFIDENTIAL

Visit Identifier	Screening	Baseline (Day 1)	Day 5	Day 10	Day 14	Day 21	Day 34	ET	Notes
Visit Window	Day -1 to Day 1	0 days	0 days	±1 day	±2 days	±2 days	±3 days		
Type of Visit	In-Person Site or Home Health Visit with Telehealth	In-Person Site Visit	In-Person Site or Home Health Visit	Telehealth Visit	In-Person Site, Home Health or Telehealth Visit	Telehealth Visit	In-Person Site, Home Health or Telehealth Visit	In-Person Site, Home Health or Telehealth Visit	

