Pregnancy test ( $\beta$ -hCG)	X						X	X	
 
• A negative urine pregnancy test must be confirmed at screening and prior to dispensing treatment for all WOCBP. Pregnancy tests will also be done whenever 1 menstrual cycle is missed during the active treatment period (or when potential pregnancy is otherwise suspected) and at Day 34 ±3 or ET visit.
 
• Local urine testing (ie, at the site, home, etc) will be standard for the protocol unless serum testing is required by local regulation or IRB/EC or the participant is anuric.
 
• See Section 8.3.5, Appendix 2 and Appendix 4.
 

HIV test (Germany only)	X								
 
• Local HIV testing at screening will be performed for participants in Germany as required by the German HA.
 
• See Appendix 2 and Appendix 9.
 

Rapid antigen testing	X								
 
• Only required if a participant does not have results of a positive SARS-CoV-2 test that was obtained within 5 days prior treatment assignment.
 
• See Section 5.1.
 

CCI									

PFIZER CONFIDENTIAL

Visit Identifier	Screening	Baseline (Day 1)	Day 5	Day 10	Day 14	Day 21	Day 34	ET	Notes
Visit Window	Day -1 to Day 1	0 days	0 days	±1 day	±2 days	±2 days	±3 days		
Type of Visit	In-Person Site or Home Health Visit with Telehealth	In-Person Site Visit	In-Person Site or Home Health Visit	Telehealth Visit	In-Person Site, Home Health or Telehealth Visit	Telehealth Visit	In-Person Site, Home Health or Telehealth Visit	In-Person Site, Home Health or Telehealth Visit	
Specified biomarker research (plasma)		X	X		[X]		[X]	[X]	
CCI
 
 
Samples will be collected at Day 1 and Day 5 for all participants.
 
If an in-person (site or home health) visit is conducted, this sample should be collected at Day 14 ±2 days, Day 34 ±3 days and ET visits.
 
See Section 8.7.2.1.
 

Retained Research Samples for biomarkers (Prep B2.5)		X	X		[X]		[X]	[X]	
 
Samples will be collected at Day 1 and Day 5 for all participants.
 
See Section 8.7.3.
 
If an in-person (site or home health) visit is conducted, this sample should be collected at Day 14 ±2 days, Day 34 ±3 days or ET visits.
 

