Participant-completed electronic diary (study intervention log)		Day 1 through Day 5							
 
The electronic diary will be provided or application downloaded to participant's own device and training completed at the Baseline visit.
 
Daily dosing will be entered in an electronic diary Days 1 through Day 5. The Day 1 dose at the site should be entered in the eDiary by the participant (or caregiver) while on site.
 
For participants who are using an eDiary provided through the study, the eDiary will be collected on Day 5, the next scheduled visit or ET visit after completion of dosing log entries on the device.
 

PFIZER CONFIDENTIAL

Visit Identifier	Screening	Baseline (Day 1)	Day 5	Day 10	Day 14	Day 21	Day 34	ET	Notes
Visit Window	Day -1 to Day 1	0 days	0 days	±1 day	±2 days	±2 days	±3 days		
Type of Visit	In-Person Site or Home Health Visit with Telehealth	In-Person Site Visit	In-Person Site or Home Health Visit	Telehealth Visit	In-Person Site, Home Health or Telehealth Visit	Telehealth Visit	In-Person Site, Home Health or Telehealth Visit	In-Person Site, Home Health or Telehealth Visit	
Investigational Site check of participant eDiary dosing entries		Day 1 through Day 5							
 
On Days 1-5, site personnel will review eDiary participant dosing entries daily on the Trial Manager portal and contact participant if not completed.
 
See Section 6.5.
 

Record HD Details (Cohort 2 only)		HD Days during Day 1 through Day 5							
 
During HD treatment, site staff should record relevant HD details on the designated CRF.
 

Retrieval of unused study intervention and empty study intervention containers			X		[X]			[X]	
 
If the Day 5 visit is conducted prior to last dose of study intervention on Day 5, empty study intervention containers, and unused study intervention should be returned at the next in-person visit (Day 14). The electronic diary should be reviewed and device should be returned if applicable.
 
See Section 6.5.
 

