PF-07321332 (nirmatrelvir)/ritonavir was generally safe and well-tolerated in both healthy and renally impaired adult participants. The number of all-causality TEAEs were similar between the mild (1 AE), moderate (1 AE) and normal renal function (3 AEs) groups. All AEs in these 3 groups were mild and not considered treatment related. A greater number of participants in the severe renal impairment group experienced TEAEs (17 AEs experienced by 5 participants in the severe renally impaired group). Of these 17 AEs, 4 (dry mouth and dysgeusia) were considered treatment related. There were 3 SAEs occurring in 1 participant in the severe renally impaired group, including 1 SAE of acute kidney injury, which resulted in study withdrawal. None of the AEs or SAEs were considered treatment related in this participant. There were no clinically meaningful laboratory findings or trends observed in this study.

The proposed dose is being developed based on internal analysis of data on file using population PK modeling. This analysis demonstrated the CL was reduced by 1/3. This was based on PK modeling using draft data from renally impaired subjects enrolled in the C467 program which included 4 subjects from Study C4671005. Of note, these participants did not experience significant safety events while on study. The data from PK modeling has supported the use of a reduced dose in severe renal impaired participants with COVID-19.

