### **8.3.4. Clinical Safety Laboratory Assessments**

See [Appendix 2](#) for the list of clinical safety laboratory tests to be performed and the [SoA](#) for the timing and frequency. All protocol-required laboratory assessments, as defined in [Appendix 2](#), must be conducted in accordance with the laboratory manual and the [SoA](#). Unscheduled clinical laboratory measurements may be obtained at any time during the study to assess any perceived safety issues.

Laboratory safety parameters will be graded according to DAIDS Table for Grading the Severity of Adult and Pediatric Adverse Events, version 2.1. The investigator must review the laboratory report, document this review, and record any clinically significant changes occurring during the study in the AE section of the CRF. Clinically significant abnormal

laboratory test findings are those that are not associated with the underlying disease, unless judged by the investigator to be more severe than expected for the participant's condition.

All laboratory tests with values considered clinically significant and abnormal during participation in the study or within 28 days after the last dose of study intervention should be repeated until the values return to normal or baseline or are no longer considered clinically significant by the investigator or study medical monitor.

If such values do not return to normal/baseline within a period of time judged reasonable by the investigator, the etiology should be identified and the sponsor notified.

See [Appendix 6](#) for suggested actions and follow-up assessments in the event of potential DILI.

See [Appendix 7](#) for instructions for laboratory testing to monitor kidney function and reporting laboratory test abnormalities.

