## **10.6. Appendix 6: Liver Safety: Suggested Actions and Follow-Up Assessments and Study Intervention Rechallenge Guidelines**

### **Potential Cases of Drug-Induced Liver Injury**

Humans exposed to a drug who show no sign of liver injury (as determined by elevations in transaminases) are termed “tolerators,” while those who show transient liver injury but adapt are termed “adaptors.” In some participants, transaminase elevations are a harbinger of a more serious potential outcome. These participants fail to adapt and therefore are “susceptible” to progressive and serious liver injury, commonly referred to as DILI.

Participants who experience a transaminase elevation above  $3 \times$  ULN should be monitored more frequently to determine if they are “adaptors” or are “susceptible.”

In the majority of DILI cases, elevations in AST and/or ALT precede T bili elevations ( $>2 \times$  ULN) by several days or weeks. The increase in T bili typically occurs while AST/ALT is/are still elevated above  $3 \times$  ULN (ie, AST/ALT and T bili values will be elevated within the same laboratory sample). In rare instances, by the time T bili elevations are detected, AST/ALT values might have decreased. This occurrence is still regarded as a potential DILI. Therefore, abnormal elevations in either AST OR ALT in addition to T bili that meet the criteria outlined below are considered potential DILI (assessed per Hy’s law criteria) cases and should always be considered important medical events, even before all other possible causes of liver injury have been excluded.

The threshold of laboratory abnormalities for a potential DILI case depends on the participant’s individual baseline values and underlying conditions. Participants who present with the following laboratory abnormalities should be evaluated further as potential DILI (Hy’s law) cases to definitively determine the etiology of the abnormal laboratory values:

- Participants with AST/ALT and T bili baseline values within the normal range who subsequently present with AST OR ALT values  $\geq 3 \times$  ULN AND a T bili value  $\geq 2 \times$  ULN with no evidence of hemolysis and an alkaline phosphatase value  $<2 \times$  ULN or not available.
- For participants with baseline AST **OR** ALT **OR** T bili values above the ULN, the following threshold values are used in the definition mentioned above, as needed, depending on which values are above the ULN at baseline:

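### Safety labs at Day 14, Day 34 and ET depend on the previous sample, so a participant who withdraws from the study before Day 5 may have no required post-dose panel

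*Protocol*

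**What the plan says.** **Protocol 1.3, laboratory notes.** Hematology and chemistry carry an unbracketed mark only on Day 1 and Day 5. The Day 1 sample is pre-dose: "Baseline laboratory assessments should be collected prior to first dose of study intervention". For later visits: "Safety laboratory tests (hematology, blood chemistry) at Days 14±2 and 34±3/ET are required only if clinically significant abnormal laboratory values were present" in the sample from the last visit at which labs were done. The general note on bracketed items says that, after Day 1, they are done at in-person visits and where the SoA requires them.

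**Same visits, other blood.** Serology has no abnormality condition: "SARS-CoV-2 serology sample should be collected if an in-person (in clinic or home health) visit is conducted at Day 14±2, Day 34±3 or ET". Nor does biomarker plasma: at an in-person visit, "this sample should be collected at Day 14 ±2 days, Day 34 ±3 days and ET visits". The retained biomarker sample follows the same pattern. Day 14, Day 34 and ET may each be telehealth.

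**Day 5 timing.** The row on drug retrieval provides for the Day 5 visit coming before the final dose: "If the Day 5 visit is conducted prior to last dose of study intervention on Day 5".

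**Protocol 8.3.4.** The section defines which abnormal values count as clinically significant: "laboratory test findings are those that are not associated with the underlying disease, unless judged by the investigator to be more severe than expected". Such values found up to 28 days after the last dose are to be repeated. Unscheduled tests may be done at any time for a perceived safety issue.

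**Protocol 10.7.1 (Appendix 7).** Standard kidney safety monitoring is said to need creatinine at baseline and again after baseline.

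**Protocol 7.1.** Stopping study drug is not withdrawal from the study; the participant stays for the remaining scheduled assessments.

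**SAP 6.6.2 and Appendix 2.1.** Laboratory values over time are summarized for Days 1 and 5. Unplanned results are listed and can enter the abnormality tables.

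**The concern.** The primary objective is safety and tolerability, followed to Day 34. Under Appendix 3 of the protocol, a clinically significant laboratory change can be an adverse event, but a change without symptoms is counted only if someone measures it. For a participant who withdraws before Day 5, the sample that decides whether ET labs are needed was taken before any drug was given, so it carries no information about the effect of treatment. For participants with an unremarkable Day 5 panel, the schedule contains no later laboratory check. In both cases the protocol asks for serology and research blood whenever the visit is in person, so a blood draw can take place without the safety tubes.

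**Working it through.** The plan states no figure on this point, so there is none to reproduce. The check follows the rule through each route a participant can take.

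| Route | Sample that decides | Required post-dose hematology/chemistry panels |
|---|---|---|
| A. Withdraws from study before Day 5, baseline without clinically significant abnormality | Day 1, pre-dose | 0 |
| B. Reaches Day 5, no clinically significant abnormality | Day 5 | 1 (Day 5 only) |
| C. Reaches Day 5, clinically significant abnormality | Day 5, then Day 14 | Day 5 and Day 14, plus Day 34 if Day 14 is still abnormal |
| D. Stops drug but stays in study | As B or C | As B or C, because Section 7.1 keeps the Day 5 labs |

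**Route A against Appendix 7.** The appendix needs two creatinine values, one after baseline. Route A guarantees only the first. A Cohort 2 participant who leaves after the sampled dialysis session will have a post-dose hematocrit, but no chemistry.

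**Route B, time without a required panel.** 34 − 5 = 29 days; with the ±3-day window, 31 − 5 = 26 to 37 − 5 = 32 days.

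**Route B against Section 8.3.4.** The repeat rule covers values found up to 28 days after the last dose, which for a Day 5 last dose is Day 5 + 28 = Day 33. On Route B no scheduled test after Day 5 can produce a value for that rule to act on.

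**Day 5 sample and exposure.** Protocol Table 1 gives a half-life of 13.37 h (SD 3.3225) after a single dose in participants not on dialysis. Taking five half-lives as the usual convention for washout:
- mean: 5 × 13.37 = 66.9 h (2.8 days);
- mean − 1 SD: 5 × 10.05 = 50.2 h (2.1 days);
- mean + 1 SD: 5 × 16.69 = 83.5 h (3.5 days).

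A Day 5 sample therefore comes before washout and may follow only four of the five doses. This is context for Cohort 1; it should not be carried over to dialysis or read as a multiple-dose figure.

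**What testing everyone could show (assumed rates).** The documents give no rate of new laboratory abnormality after Day 5. With an assumed rate p and n participants tested, P(at least one case) = 1 − (1 − p)^n.

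| p (assumed) | n = 12 | n = 24 |
|---|---|---|
| 5% | 0.46 | 0.71 |
| 10% | 0.72 | 0.92 |
| 20% | 0.93 | 0.995 |

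These are upper figures, because they assume that all are tested. On Route B such a case is found only through symptoms or an unscheduled test.

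**The case against.** Follow-up triggered by risk after five days of dosing is a legitimate design. The wording is about what is required, not what is allowed. Adverse events are monitored at every visit to Day 34, the investigator may order tests at any time, and a clinically significant Day 5 result brings repeat panels. Appendix 7 reads partly as general guidance, since it also allows for studies in which kidney tests are not routine. All of this stands, and it limits the point. It does not close Route A: an unscheduled test needs a perceived issue, and a silent change gives none.

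A reader might also infer several stronger claims that the documents do not support:

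- **Nobody is checked after Day 5.** Route C and continued adverse event monitoring show otherwise.
- **A participant with acute kidney injury would leave untested.** Section 2.2.1 reports from the earlier renal study: "There were 3 SAEs occurring in 1 participant in the severe renally impaired group, including 1 SAE of acute kidney injury". But the same SoA notes require abnormal values related to adverse events to be followed to resolution, so a recognized injury is covered. Section 2.2.1 also says that the events in that participant were not considered treatment related and that no meaningful laboratory trends were seen. The adverse event counts there do not show missed labs.
- **Liver injury would first appear after Day 5.** Appendix 6 says: "In the majority of DILI cases, elevations in AST and/or ALT precede T bili elevations". That describes the lag between two markers, not the time of first onset.
- **The trigger seldom operates in this population.** Section 8.3.4 narrows it, but keeps findings worse than expected for the condition. No document gives a frequency.

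**Conclusion.** The point holds in a limited form. A participant who leaves the study before Day 5 with an unremarkable baseline has no required post-dose safety panel, because the deciding sample predates exposure. A participant with an unremarkable Day 5 panel has one post-dose panel and none required for a further 29 days (26 to 32). The first gap is the more serious, because it sits badly with Appendix 7 and leaves a treated participant with no laboratory change from baseline.

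The number affected cannot be estimated from the documents: neither the rate of withdrawal before Day 5 nor the share of telehealth visits is given. One such withdrawal is 1/12 = 8.3% of a cohort, or 1/24 = 4.2% of the study. Any undercount of laboratory-based events is therefore possible but unquantified. The conclusion assumes that the specific laboratory note governs the bracketed marks. If the sponsor meant the brackets alone to require panels at every in-person visit, the note contradicts that and needs rewording anyway.

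**What to change.** Reconcile the laboratory note in Protocol 1.3 with Section 8.3.4 and Appendix 7:

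1. For withdrawal from the study before Day 5, do not make the ET panel depend on the pre-dose sample.
2. At any in-person (site or home health) Day 14, Day 34 or ET visit where serology or biomarker blood is drawn, add the hematology and chemistry tubes whatever the previous result.
3. In the SAP, include these results in the abnormality tables and listings. If Day 14 and Day 34 values are also summarized over time, show n and state that they come only from participants seen in person. That group is selected, partly because an earlier abnormality can itself bring a participant in.

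**Cost.** A reworded note, a short SAP addition, a laboratory charge and a few mL of blood at draws that already take place. Section 8.1 plans about 120 mL (Cohort 1) and 150 mL (Cohort 2) against a 550 mL limit, leaving about 430 and 400 mL. Item 2 needs no new visit or venipuncture.

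**What remains.** Participants seen only by telehealth, including those who decline an in-person ET visit, are still not covered. The report should say how many treated participants have no post-dose panel.

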**PK SAMPLING SCHEMA 1 – COHORT 1: Severe Renal Impairment not on HD**

Study Day	1	2	3	4		5		
PF-07321332 (nirmatrelvir)/ritonavir administration	X	X	X	X		X a		
Hours after doseb	1-3	4-8	9 to 15	0	1-4	0	0.5-6	9 to 15
PK blood sampling (Tasso)	X c	X c	X c	X d	X c	X d	X c	X c
Blood:Plasma Ratio sample (venous)	X e		[X e ]	[X e ]		[X e ]		

- a. For Day 5 in-person (site or home health) visit:
- If the time of the scheduled visit is within the dosing window ( $\pm$  4 hours), participants should wait to take the dose of PF-07321332 (nirmatrelvir)/ritonavir during the in-person visit. The dose will be taken after the pre-dose PK sample has been obtained and thereafter PK samples will be obtained according to the PK timepoint schedule;
  - If the time of the scheduled visit is not within the dosing window ( $\pm$  4 hours), participants should take the dose of PF-07321332 (nirmatrelvir)/ritonavir at the participant's usual time and PK samples will be obtained according to the PK timepoint schedule.
- b. Hours are in reference to the QD dose of PF-07321332 (nirmatrelvir)/ritonavir on each study day. The Day 1 dose should be taken at the clinic visit.
- c. Tasso blood sample: After dosing study drug, Tasso device placed by participant, caregiver, home health provider, or other healthcare provider (as appropriate).
- d. Tasso blood sample: Prior to dosing study drug, Tasso device placed by participant, caregiver, home health provider, or other healthcare provider (as appropriate).
- e. Blood:Plasma Ratio venous sample: Collect immediately before or after the Tasso sample but no longer than 15 minutes between the samples. The blood:plasma ratio sample tube is divided into 1 blood sample (in a cryovial) and, after centrifugation, 1 plasma sample (in another cryovial) (reference the Central Lab Manual). Collect first sample on Day 1 and second sample either on Day 3 or Day 4 or Day 5. It is advised to have second sample collected on Day 5, given the need for in-person visit.

**PK SAMPLING SCHEMA 2 – COHORT 2: HD cohort with 1st Dose on HD day that is Monday**

Study Day	Day 1 – HD MONDAY	Day 2 – no HD TUESDAY	Day 3 – HD WEDNESDAY	Day 4 – no HD THURSDAY				Day 5 – HD FRIDAY
PF-07321332 (nirmatrelvir)/ritonavir administration	X b	X	X b		X			X b
Hours after dosea	1 – 3		Before and During HD	0	0.5 – 3	4 – 8	9 – 15	Before HD start
PK blood sampling (Tasso)	X f		X c	X c	X f	X f	X f	[X c ]
PK blood sampling during HD (arterial and venous ports)			X d					X e
Hematology blood sample (hematocrit)			X i					
Blood:Plasma Ratio sample (venous)	X h		X g, h		X h			[X g, h ]

- a. Hours are in reference to the QD dose of PF-07321332 (nirmatrelvir)/ritonavir on each study day. The Day 1 dose should be taken at the clinic visit.
- b. On dialysis days, participants will take study intervention as soon as feasible after HD.
- c. Tasso blood sample: Tasso device placed by participant, caregiver, home health provider, or other healthcare provider (as appropriate).
- d. Venous blood samples: HD staff to obtain PK blood samples from the HD filter arterial port and the venous port at 0 hr (prior to start of HD) and at 0.5, 1, 2, 3, and 4 hours post start of dialysis.
- e. Day 5 PK blood sample: If participant goes to HD treatment prior to going to investigational site on Day 5, then HD staff to obtain this venous sample prior to the start of dialysis from the venous HD line. If participant goes to investigational site prior to going to HD on Day 5, then investigational site staff can obtain PK sample using the Tasso device.
- f. Tasso blood samples: After dosing study drug, Tasso device placed by participant, caregiver, home health provider, or other healthcare provider (as appropriate). Collect the consecutive PK samples within the prescribed windows with each sample taken a minimum of 2 hours apart.
- g. Blood:Plasma Ratio venous sample: Collect at 0 hr prior to start of HD.
- h. Blood:Plasma Ratio venous sample: Collect immediately before or after a Tasso sample but no longer than 15 minutes between the samples. The blood:plasma ratio sample tube is divided into 1 blood sample (in a cryovial) and, after centrifugation, 1 plasma sample (in another cryovial) (reference the Central Lab Manual). Collect blood:plasma ratio samples on Day 1 and Day 3. If one sample is missed, it may be collected on Day 4 or Day 5. Always collect a corresponding Tasso sample for each blood:plasma ratio sample.
- i. Hematocrit: Obtain 2 hematology blood samples (hematocrit) - one at time 0 hr (venous port sample) and one time of the last PK draw (venous port sample) during HD (hematocrit needed for CLd calculations).

